# 8.5.1.10 Overall Survival (OS)

OS is defined as time from the first date of study treatment to the date of death due to any cause. If a subject has not died, then the data will be censored on the date when the subject was last known alive.

The last known alive date will be determined by selecting the last available date of the following study procedures: last dose date of study treatment, start date of adverse event, bone marrow collection, disease assessment, spleen assessment, vital signs assessment, electrocardiogram assessment, clinical laboratory collection (including COVID-19 test), study drug administration, start date of concomitant or post-treatment medicine or procedure, last known alive date in survival follow-up, biospecimen sample collection, quality of life assessments, and performance status.

OS will be analyzed in the Full Analysis Set.

#### 8.5.1.11 Change in PROMIS Fatigue Score

Change in PROMIS fatigue score is defined as the change from baseline score by Visit. The scores are collected using PROMIS Fatigue SF7a. The summary score, symptom and impact scores will be calculated according to the scoring algorithm specified in Appendix C. Data after the start of post-study treatment, disease progression will not be included in the analyses. Change in PROMIS Fatigue Score will be analyzed among subjects who had baseline and post-baseline PROMIS Fatigue Score.

#### 8.5.1.12 Change in EORTC QLQ-C30 Score

Change in EORTC QLQ-C30 score is defined as the change from baseline score by Visit. The scores are collected using EORTC QLQ-C30. The summary score of EORTC QLQ-C30 will be calculated according to the scoring algorithm specified in Appendix C. Data after the start of post-study treatment, disease progression will not be included in the analyses. Change in EORTC QLQ-C30 Score will be analyzed among subjects who had baseline and post-baseline EORTC QLQ-C30 score.

[figure not shown]
#### 8.5.2 Main Analyses of Exploratory Efficacy Endpoints

The data will be analyzed per Section 8.1.

#### 8.6 Additional Efficacy Analyses

# 8.6.1 Change in Variant Allele Frequency

Change from baseline in variant allele frequency any time during the post baseline period will be derived by specific driver gene, which is mutated-JAK2, -CALR, and -MPL, if baseline allele frequency and post-baseline allele frequency are available based on the Next Generation Sequencing (NGS) method in the peripheral blood. Data after the start of post-study treatment, disease progression WILL BE included in the analyses. Change in variant allele frequency will be analyzed among subjects who had baseline and post-baseline variant allele frequency.

Proportion of subjects achieving allele frequency reduction from baseline of  $\geq$  20% at Week 24 or any time during the study treatment will be summarized among subjects with baseline and post-baseline of variant allele frequency for Cohort 1a, Cohort 1b and Cohort 3. Maximum percentage reduction from baseline in allele frequency will be presented by the waterfall plot for all cohorts.

#### 8.6.2 Main Analyses of Additional Endpoints

Descriptive statistics with visit mean, mean change from baseline, mean percentage change from baseline, standard deviation and range will be provided.

## 8.7 Efficacy Subgroup Analyses

Subgroup analyses will be performed for the primary SVR35W24 endpoint.

The following subgroups will be used (but not limited to):

- type of MF (Primary MF and Secondary MF)
- DIPSS risk at study entry (Inetermediate-1, Intermediate-2 and High risk).
- Age  $(18 < 65 \text{ years}) \ge 65 \text{ years})$

[figure not shown]
# 9.0 Safety Analyses

#### 9.1 General Considerations

Safety data will be summarized using the Safety Analysis Set defined in Section 4.0. The safety summaries will be presented by Cohort. For all safety analyses, unless otherwise specified, data collected up to the analysis data cutoff date will be used.

#### 9.2 Adverse Events

Adverse events (AEs) will be summarized and presented using primary MedDRA System Organ Classes (SOCs) and preferred terms (PTs) according to the version of the MedDRA coding dictionary used for the study at the time of database lock. The actual version of the MedDRA coding dictionary used will be noted in the AE tables and in the clinical

study report. Specific adverse events will be counted once for each subject for calculating percentages, unless stated otherwise. In addition, if the same adverse event occurs multiple times within a subject, the highest severity and level of relationship to investigational product will be reported.

# 9.2.1 Treatment-Emergent Adverse Events

[figure not shown]
Treatment-emergent AEs (TEAE) are defined as any AE with the onset that is on or after the first dose of navitoclax until 30 days after the last date of study drug. Events where the onset date is the same as the study drug start date are assumed to be treatment emergent. If an incomplete or missing onset date was collected for an AE, the AE will be assumed to be treatment-emergent unless there is evidence to the contrary (e.g., the AE end date was prior to the date of the first dose of study drug). All TEAEs will be summarized overall, as well as by primary MedDRA SOC and PT. The SOCs will be presented in alphabetical order, and the PTs will be presented in alphabetical order within each SOC.

The number and percentage of subjects experiencing TEAEs will be summarized.

#### 9.2.2 Adverse Event Overview

An overview of AEs will be presented consisting of the number and percentage of subjects experiencing at least one event for each of the following AE categories:

- Any TEAE
- Any grade 3 TEAE
- Any grade 4 TEAE
- Any TEAE with grade 3, or 4
- Any TEAE with grade 3, 4 or 5
- Any serious TEAE
- Any TEAE with reasonable possibility related to navitoclax assessed by the investigator

- Any TEAE with reasonable possibility related to ruxolitinib assessed by the investigator
- Any TEAE leading to discontinuation of navitoclax
- Any TEAE leading to discontinuation of ruxolitinib
- Any TEAE leading to interruption of navitoclax
- Any TEAE leading to interruption of ruxolitinib
- Any TEAE leading to dose reduction of navitoclax
- Any TEAE leading to dose reduction of ruxolitinib
- Any TEAE leading to death
- All deaths
- Deaths occurring  $\leq 30$  days after last dose of navitoclax
- Deaths occurring > 30 days after last dose of navitoclax

[figure not shown]

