5.1 Overall Study Design and Plan: Description

This is a Phase 2, multicenter, open-label study designed to evaluate the tolerability and efficacy of navitoclax alone or in combination with ruxolitinib in subjects with primary or secondary myelofibrosis (PPV-MF, PET-MF). Subjects enrolled in Cohort 1a must have received ruxolitinib therapy for at least 12 weeks and currently be on a stable dose of ≥ 10 mg twice daily of ruxolitinib. For Cohort 1b subjects must have received treatment with ruxolitinib. For Cohort 2, subjects must have received prior treatment with a JAK-2 inhibitor. For Cohort 3, subjects must not have received prior treatment with a JAK-2 inhibitor or BET inhibitor.

Approximately 174 subjects at approximately 135 sites globally will be enrolled in the following cohorts:

- Cohort 1a: 34 subjects (fully enrolled as of 10 April 2019)
- Cohort 1b: approximately 80 subjects will be enrolled to ensure enrollment of approximately 70 subjects with prior exposure to ruxolitinib.
- Cohort 2: approximately 30 subjects
- Cohort 3: approximately 30 subjects

The study is designed to meet scientific and regulatory objectives without enrolling an undue number of subjects in alignment with ethical considerations. All efforts will be made to adhere to these specific enrollment numbers; however, it might not be ethical to deny treatment to subjects in Screening as they may have undergone study related procedures. Subjects that are enrolled and do not meet the inclusion criteria as outlined in Section 5.2 may be replaced at the discretion of the Sponsor.

The study will consist of the following:

Screening: Study assessment performed prior to enrollment;

- **Treatment:** Study assessments performed from first dose through the Treatment Completion Visit (TCV);
- Follow-up:
 - Safety Follow-up: approximately 30 days following TCV to assess adverse events
 - **Post-Treatment Follow-up:** Every 12 weeks after the TCV until disease progression is documented or until another therapy for MF is initiated
 - **Survival:** Every 6 months follow-up for survival status and collection of post-treatment cancer therapy details

[figure not shown]
Screening

Unless otherwise specified, Screening assessments must be performed within 28 days prior to first dose of navitoclax. For subjects enrolled in Cohorts 1b and 3, the screening period should be long enough to ensure there is at least 7 days to collect the daily MFSAF v4.0 prior to Day 1.

Treatment

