# 6.3 Subject-Years of Exposure

Subject-years of study drug exposure is calculated as below for navitoclax and ruxolitinib, respectively:

Subject-years of exposure (sub-yr) = 
$$\frac{\text{Sum of duration of study drug for all subjects (days)}}{365.25}$$

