# 11.0 Interim Analyses

[figure not shown]
There is no planned interim analysis. However, when all subjects from each Cohort complete Week 24 disease assessment, or discontinue from study, whichever occurs first, primary efficacy analysis will be performed for the corresponding Cohort along with summaries for efficacy and safety data from other cohorts.

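### The main by-cohort AE and worst-grade laboratory tables are crude cumulative percentages with no common follow-up window, so late or accumulating events will tend to look more frequent in longer-followed cohorts

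*SAP*

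**What the plan says.** SAP 9.1 sets the layout ("The safety summaries will be presented by Cohort") and the data span: "data collected up to the analysis data cutoff date will be used", unless otherwise specified. The overview in SAP 9.2.2 is "presented consisting of the number and percentage of subjects experiencing at least one event for each of the following AE categories". It has 18 categories, including serious events, discontinuations, dose reductions and deaths. SAP 9.2.3 and 9.2.4 carry the same counting into the SOC/PT, maximum-grade and SAE tables. SAP 9.3.1 cross-tabulates baseline grade mainly against the highest grade seen after the first dose.

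SAP 9.2.1 counts an event as treatment-emergent up to 30 days after the last dose, and the laboratory shift tables stop at the same point. Treatment itself has no fixed length (Protocol 5.1).

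SAP 11.0 fixes the cuts cohort by cohort: "when all subjects from each Cohort complete Week 24 disease assessment, or discontinue from study, whichever occurs first, primary efficacy analysis will be performed" for that cohort, "along with summaries for efficacy and safety data from other cohorts". Protocol 5.1 records Cohort 1a as full by 10 April 2019.

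On exposure, SAP 6.3 states: "Subject-years of study drug exposure is calculated as below for navitoclax and ruxolitinib, respectively". No AE or laboratory rate in the SAP uses that total as a denominator.

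**The concern.** The proportion of subjects with at least one event can only stay level or rise as follow-up lengthens, and so can a worst grade. When one cohort reaches its Week 24 cut, the plan prints its percentages beside those of cohorts with a different length of follow-up. Nothing in the main tables puts the columns on the same footing.

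A reader will set monotherapy (Cohort 2) against combination, or Cohort 1a with its 50 mg start against the later cohorts starting at 100 or 200 mg. Part of any difference in SAEs, infections, discontinuations or deaths may then be follow-up time rather than regimen. There is no independent data monitoring committee (SAP 11.1), so these descriptive tables are what the sponsor's own safety review has to hand. The protocol already draws on such percentages: its dose rationale (Protocol 5.6.3) cites the 83% of Cohort 1a subjects with a navitoclax dose reduction.

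**Working it through.** **The plan's own safety figure.** Protocol 8 and SAP 2.4 assume a 10% chance of an SAE due to study treatment. The chance of seeing at least one is 1 − 0.9^n: 97.22% for n = 34, 99.98% for n = 80 and 95.76% for n = 30. These agree with the stated bounds of 97%, 99% and 95%. The 10% is given with no period attached, so it too is a cumulative probability over unspecified follow-up.

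**How far follow-up can differ.** From 10 April 2019 to 28 February 2020 (the date of the Cohort 1a data in Protocol 3.4) is 324 days, or 46.3 weeks. To the SAP 4.0 date, 31 January 2023, is 1,392 days, or 198.9 weeks. These are minimum calendar times since enrolment for Cohort 1a, not time on drug. A subject who has just triggered another cohort's cut by completing Week 24 has 24 weeks.

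**What unequal follow-up does to a crude percentage.** The inputs here are assumptions: the same constant weekly hazard λ in every cohort, all subjects cut at time t, and exponential discontinuation at rate d = ln 2 / median. The 30-day tail after the last dose is ignored.

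- λ = −ln(1 − 0.10)/24 = 0.00439 per week, which gives 10% by Week 24 if nobody stops.
- Crude proportion without discontinuation: 1 − exp(−λt).
- Crude proportion with discontinuation: λ/(λ+d) × [1 − exp(−(λ+d)t)].
- Rate per 100 subject-years: 0.00439 × 52.18 × 100 = 22.9.

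| Median time to discontinuation | Crude % at 24 wk | 48 wk | 96 wk | Rate per 100 subject-years |
|---|---|---|---|---|
| None stop | 10.0 | 19.0 | 34.4 | 22.9 |
| 96 wk | 9.2 | 16.2 | 25.4 | 22.9 |
| 48 wk | 8.5 | 13.9 | 19.5 | 22.9 |
| 24 wk | 7.3 | 10.5 | 12.7 | 22.9 |

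With 20% by Week 24 and no discontinuation, the crude values are 20.0, 36.0 and 59.0%, against a steady 48.5 per 100 subject-years. Events confined to the first weeks would show almost no rise.

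**What the plan already has against this.**

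- SAP 9.2.5.2 defines incidence by time period among subjects dosed in that period without an earlier event. The tables are optional; the plot for each search is a commitment. Scope: the safety topics of interest in SAP Appendix E.
- SAP 9.2.5.1 summarises time to onset for those topics, and time to the first TEAE leading to dose reduction or interruption. These are means, medians and ranges, not rates.
- SAP 9.3.2 draws box plots of eight laboratory parameters at fixed weeks, not worst grade.
- SAP 8.5.1.6 gives PRBC transfusions per subject-month.
- SAP 8.5.1.10, with SAP 8.1, gives Kaplan-Meier overall survival by cohort.

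Left without a common window or a time denominator are SAEs overall, discontinuations, the full SOC/PT and maximum-grade tables, worst laboratory grade, and the crude death counts. Two of the death categories, all deaths and deaths more than 30 days after the last dose, are not bounded by the TEAE window.

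**The case against.** The strongest reply is that the plan handles its most important toxicities by time: thrombocytopenia, neutropenia, hemorrhage, serious infections, liver injury and malignancy all get the period-specific plot with an at-risk denominator. That stands. A reader might infer that every safety output ignores follow-up, and the documents do not support that.

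It is also fair that calendar time is not risk time. The TEAE and laboratory windows close 30 days after the last dose, so early discontinuation limits the inflation. Protocol 3.3 says platelet nadirs typically come in the first few days of dosing. A reader might therefore go too far in concluding that longer-followed cohorts must look more toxic; it is a tendency whose strength depends on the event.

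A reader might also try to size the gap from the 13/34 (38%) of Cohort 1a subjects with an SAE. Spreading these at a constant hazard over an assumed mean of 46, 60 or 80 weeks gives 22, 18 or 14% at 24 weeks, an apparent gap of 16 to 25 points. That is not supportable. It sets an assumed mean exposure in one cohort against exactly 24 weeks for everyone in another, whereas SAP 11.0 waits for the last subject. With an assumed 52 weeks of uniform accrual and no discontinuation, follow-up in the newer cohort runs from 24 to 76 weeks. The expected crude proportion, 1 − [exp(−24λ) − exp(−76λ)]/(52λ), is then about 40, 33 or 26% on the same hazards, and the gap about −2, 6 or 13 points.

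Finally, no between-cohort test is planned (Protocol 8.3), the objective is to describe safety, and the cohorts differ in prior therapy, platelet eligibility, starting dose and ruxolitinib use. This confines the harm to descriptive side-by-side reading, but by-cohort tables invite that reading.

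**Conclusion.** The point holds for the main by-cohort tables: overview, SOC/PT, SAE, maximum grade and worst-grade laboratory shifts. They are cumulative percentages to the cutoff, follow-up is unequal by design, and subject-years never become an AE or laboratory rate. The time-based displays in SAP 9.2.5 cover only part of the gap.

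The direction is a tendency, strongest for late or accumulating events and slight for early ones. The size is unknown, since neither exposure nor accrual by cohort is given. The illustrative range (10% becoming 34.4% between 24 and 96 weeks with no discontinuation, or 7.3% becoming 12.7% with a median of 24 weeks to discontinuation) rests on a constant hazard, a common cut time and assumed event and discontinuation rates. It shows that the effect can be material; it does not estimate it for this trial. No planned test or primary efficacy result is touched. This is an inexpensive improvement to the safety reporting.

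**What to change.** In SAP 9.2.2 to 9.2.4 and 9.3.1, add by cohort:

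- **First-24-week tables.** The overview, SAE and worst-grade laboratory tables, restricted to events and values in the first 24 weeks from the first navitoclax dose, among subjects whose first dose was at least 24 weeks before the cutoff.
- **Exposure-adjusted rates.** Rates per 100 subject-years for the key AE categories. Count subject-years over the TEAE window of SAP 9.2.1, ending at the first event where the numerator is subjects with an event.

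Make the incidence tables in SAP 9.2.5.2 mandatory, alongside the plot already promised. State that any descriptive cross-cohort safety remark will rest on these outputs, with a note that the cohorts also differ in population and regimen. Keep the existing tables.

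The cost is a few extra tables and one new derivation: SAP 6.2 and 6.3 count only from first to last dose, so the 30-day tail and the stop at first event must be added. The exposure-adjusted rates are read most easily under a roughly constant hazard; the 24-week tables do not need that assumption, which is why the two are paired.

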# 9.2.3 Treatment-Emergent Adverse Events by MedDRA SOC and/or PT

TEAEs listed in Section 9.2.2 will be summarized by MedDRA SOC and PT; Specific adverse events will be counted once for each subject for calculating percentages, unless stated otherwise. In addition, if the same adverse event occurs multiple times within a subject, the highest grade and level of relationship to investigational product will be reported.

In addition, TEAEs will be summarized by PT and sorted by decreasing frequency for Cohort 1, and summarized by MedDRA SOC, PT and maximum NCI CTCAE grade.

# 9.2.4 SAEs (including deaths) and Adverse Events Leading to Death

SAEs (including deaths) and AEs leading to death will be summarized by MedDRA SOC and PT and in listing format.

#### 9.2.5 Safety Topics of Interest

Safety topics of interest will be identified using the search criteria in Appendix E.

Selected AEs will be summarized by SOC and PT. The same overview summary as for TEAEs and a listing of subjects' data will be provided for each search.

In addition to the searches listed in Appendix E, the torsade de pointes/QT prolongation search will be provided. Following analysis may be provided using SMQ Torsade de Pointes/QT Prolongation (Broad) search criteria: The incidence of the events by preferred term, the same overview summary as for TEAEs and a listing of subjects' data.

[figure not shown]
#### 9.2.5.1 Time to Onset

Time to onset of the safety topics of interest will be summarized using summary statistics (N, mean, standard deviation, median, minimum, and maximum). Time to onset is defined as the time from first dose of Navitoclax to the first occurrence of the event. Time to onset will be summarized for each defined event as well as first Grade  $\geq 3$  event. The distribution of time to onset will be summarized for the time period as described in Section 6.2. The time periods may be adjusted to account for sparse data in later time periods if necessary.

Additionally, summary statistics (number of subjects, mean, standard deviation, median, minimum, and maximum) will be generated for time (in days) to first TEAE leading to dose reduction and time (in days) to first TEAE leading to dose interruption.

#### 9.2.5.2 Incidence and Prevalence by Time

Incidence and prevalence for each PT within the search and overall incidence may be provided for the time periods based on time from Day 1 of the study treatment to the occurrence of the event described in Section 6.2. The 30 days TEAE window will be applied and grouped into the last time period for each subject. The time periods may be adjusted to account for sparse data in later time periods if necessary.

For each time period, the incidence for any given PT will be calculated as follows:

- The numerator for each time period will be the number of subjects who had the first occurrence of an adverse event in that time period
- The denominator for each time period will be the number of subjects who took at least one dose of navitoclax in the time period and did not experience an event within any previous period
- Incidence for each time period = numerator/denominator.

[figure not shown]
For each time period, the prevalence for any given PT will be calculated as follows:

- The numerator for each time period will be the number of subjects who had an occurrence of an adverse event in that time period or in a previous time period and that was ongoing in the current time period
- The denominator for each time period will be the number of subjects who took at least one dose of navitoclax in the time period.
- Prevalence for each time period = numerator/denominator.

For each TEAE search, a plot capturing the incidence and prevalence (by time period) will be displayed.

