The guidelines noted below should be implemented for all subjects unless previously discussed and approved with the AbbVie TA MD/SD (Section 6.1.5).

If a navitoclax interruption is necessary, navitoclax may be reintroduced at the same or lower dose based on the guidance below. If a dose reduction below 50 mg once daily is required, the dose of navitoclax may be reduced to 25 mg once daily following consultation with the AbbVie TA MD/SD.

The same navitoclax dose level shall not be attempted more than twice consecutively without prior approval from the AbbVie TA MD/SD.

The local approved ruxolitinib label should be referenced for guidance on ruxolitinib dose modifications for subjects with hepatic or renal impairment, drug-drug interactions, precautions, monitoring and management of hematologic and non-hematologic toxicities.

For subjects who require interruption of ruxolitinib per the label but are considered to be at increased risk for exacerbation of splenomegaly and clinically significant symptoms, ruxolitinib dose can be tapered by the Investigator in consultation with the AbbVie TA MD/SD followed by interruption.

Decisions regarding continued dosing, including the navitoclax or ruxolitinib (if applicable) dose level to be administered, for individual subjects will be medically managed by the Investigator in consultation with the AbbVie TA MD/SD (Section 6.1.5).

Intermediate dose levels (e.g., 150 mg once daily) may be administered at the discretion of the investigator. If intermediate dose levels are utilized prior to Week 24, consultation with the AbbVie TA MD/SD is required prior to implementation.

Decisions to delay or interrupt the study treatment for active COVID-19 infection should be made by the treating investigator after considering the subject's clinical assessment of the severity of infection, current status of MF and treatment tolerance, as well as the general medical condition. Treatment interruption longer than 28 days must be discussed with the TA MD/SD.

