# 6.2 Duration of Study Drug

Duration of study drug is calculated for each subject by the following formula, for navitoclax and ruxolitinib, respectively:

Duration of study drug (days) =  $Date\ of\ the\ last\ dose\ of\ study\ drug\ -Date\ of\ the\ first\ dose\ of\ study\ drug+1.$ 

The duration of study drug will be categorized as some interval of time (e.g., every 28-day). The number and percentage of subjects in each interval will be summarized.

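### Prevalence by time period in SAP 9.2.5.2 counts subjects on a full-period navitoclax hold above the line but not below it

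*SAP*

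**What the plan says.** SAP 9.2.5.2 gives two ratios for each preferred term (PT) within a safety-topic search.

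- Prevalence. The numerator is subjects with an occurrence "in that time period or in a previous time period and that was ongoing in the current time period". For the other term: "The denominator for each time period will be the number of subjects who took at least one dose of navitoclax in the time period".
- Incidence. The numerator is "the number of subjects who had the first occurrence of an adverse event in that time period". The denominator is subjects who "took at least one dose of navitoclax in the time period and did not experience an event within any previous period".

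One rule aligns the two terms: "The 30 days TEAE window will be applied and grouped into the last time period for each subject". Period length is taken from SAP 6.2: "The duration of study drug will be categorized as some interval of time (e.g., every 28-day". SAP 9.2.5.2 also lets the periods be adjusted if later data are sparse.

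On the status of the output: "Incidence and prevalence for each PT within the search and overall incidence may be provided for the time periods". The section nevertheless ends by committing to a plot of both measures for every search.

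Two other SAP definitions bear on this. SAP 6.2 computes duration as last dose date minus first dose date plus one, with nothing deducted for interruptions. SAP 9.2.1 runs the treatment-emergent window from first navitoclax dose to 30 days after last dose, again with no gap for interruptions.

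**The concern.** A prevalence is a proportion only if everyone in the numerator is also in the denominator. Here the denominator requires dosing in the period and the numerator does not. A subject who takes no navitoclax for a whole period, and whose event has not resolved, is counted as a case but not as a person at risk.

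The loss from the denominator is not random. The protocol requires navitoclax to be interrupted for platelets below 50 × 10⁹/L and ANC below 1.0 × 10⁹/L (Appendix I), Grade 2 or higher bleeding (6.1.7.1), febrile neutropenia (6.1.7.2) and clinically significant infection (6.1.7.3). Thrombocytopenia, neutropenia, hemorrhage and serious infection are also topics in SAP Appendix E. The event being plotted can therefore be the reason the subject leaves the denominator. What is at stake is how readers see the persistence of the main toxicities over time.

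**Working it through.** The SAP states no prevalence or incidence figure, so there is none to reproduce. The check compares the two sets and then uses arithmetic on assumed counts.

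**1. Who is mismatched.** An event during a hold is treatment-emergent under SAP 9.2.1, so it can enter the numerator. With no dose in the period, the subject is outside the denominator. The 30-day rule deals with time after the last dose. It does not reach a temporary hold followed by re-dosing.

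**2. Size of the distortion, given a full-period hold.** Let N be subjects between first and last dose in the period, e those with the event, and h those of the e with no dose in the whole period.

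- As written: e/(N − h)
- All on-treatment subjects in both terms: e/N
- Dosed subjects only in both terms: (e − h)/(N − h)

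All values of e and h are assumed, since the documents give none. N = 34 is the size of Cohort 1a and N = 80 the planned size of Cohort 1b.

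| N | e | h | As written | All on-treatment | Dosed only |
|---|---|---|---|---|---|
| 34 | 10 | 0 | 10/34 = 29.4% | 29.4% | 29.4% |
| 34 | 10 | 4 | 10/30 = 33.3% | 10/34 = 29.4% | 6/30 = 20.0% |
| 80 | 40 | 4 | 40/76 = 52.6% | 40/80 = 50.0% | 36/76 = 47.4% |

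For any h above zero the written ratio exceeds both consistent versions. Subjects held for another reason and free of the event also leave the denominator, which raises the ratio further.

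**3. When a hold spans a period.** Take 28-day periods, the SAP's example, and let the hold start on any of the 28 days with equal chance. A hold of L dose-free days covers a complete period with probability (L − 27)/28, bounded at 0 and 1.

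- L up to 27: 0
- L = 28: 1/28 = 3.6%
- L = 35: 8/28 = 28.6%
- L = 42: 15/28 = 53.6%
- L = 55 or more: 1

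**4. Incidence.** The event that causes a hold normally begins before the hold, in a period with dosing, so it is counted in both terms. The mismatch needs a different PT to occur for the first time during a full-period hold. An example is febrile neutropenia arising during a hold for neutropenia; SAP Appendix E lists these as separate PTs. With N = 34, 10 earlier events, 4 new first events and 1 of those 4 undosed throughout (all but N assumed), the written ratio is 4/(34 − 10 − 1) = 4/23 = 17.4%, against 4/24 = 16.7% on the on-treatment set.

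**The case against.** The strongest reply is that the problem may never arise. No passage gives hold lengths for cytopenias. Appendix I has platelets rechecked about every 2 to 3 days during a hold, with dosing resumed at 50 × 10⁹/L, and Protocol 3.3 describes early nadirs with recovery during continued dosing. With 28-day periods, holds of up to 27 days do no harm, and wider periods would shrink the problem further. The tabulation is optional. The same toxicities also appear in the adverse event overview, subject listings, time-to-onset summaries, laboratory shift tables and box plots, none of which uses this denominator. SAP 1.0 leaves programming detail to a separate programming plan.

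All of that stands as a limit on size and importance. It does not repair the definition. Appendix I sets no maximum hold length, the plot is a commitment, and the programming plan would have to depart from the SAP's stated rule to correct it.

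A reader might also infer three stronger things that the documents do not support.

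- That the protocol expects cytopenia holds beyond four weeks, because it says "Treatment interruption longer than 28 days must be discussed with the TA MD/SD". That sentence closes a paragraph of Protocol 6.1.7 on active COVID-19 infection. It shows that long interruptions are foreseen, but not for cytopenias.
- That incidence is equally affected. Step 4 of the working shows a much narrower route.
- That the plot will exceed 100% or hide persistent toxicity. Exceeding 100% needs extreme counts, such as e = 30 and h = 5 of N = 34, giving 30/29 = 103.4%. That treats the 88% ever-incidence of thrombocytopenia in Cohort 1a as an interval prevalence. Understatement would arise only if programmers cut the numerator to dosed subjects, which the SAP does not ask for. As written, the error runs upward.

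**Conclusion.** The definition is inconsistent, clearly so for prevalence. Whenever a temporary hold spans a full period and the event is unresolved, prevalence is overstated relative to either consistent definition. The size is unknown, because hold lengths and final period lengths are not in the documents, and it is zero if no hold spans a period. On the assumed counts above, the overstatement relative to the on-treatment set is 33.3 − 29.4 = 3.9 and 52.6 − 50.0 = 2.6 percentage points. Incidence shares the mismatch only where another PT first occurs during a full-period hold.

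The output is descriptive. The primary endpoint and the overall treatment-emergent adverse event rates do not depend on it. It is worth correcting because the correction is cheap and the affected toxicities are the ones of most interest.

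**What to change.** In SAP 9.2.5.2, use one risk set in both terms: subjects for whom the span from first to last navitoclax dose, interruptions included as in SAP 6.2, overlaps the period. For incidence, also require no earlier event of that PT. Restrict each numerator to the same set.

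Keep the rule that folds the 30 days after last dose into each subject's last period, and do not extend the risk set to last dose plus 30 days. With 28-day periods that extension would put discontinued subjects into a later denominator while their events are counted earlier. For example (assumed), with 6 subjects dosed, 2 of them with the event, and 4 who stopped in the period before, it gives 2/10 = 20% instead of 2/6 = 33%.

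Dosed subjects only in both terms would also be consistent, but it removes those held because of the event and does not match SAP 6.2 or 9.2.1.

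The cost is a change of SAP wording and one programming change. No new data are needed, and no dosing or toxicity rule is touched.
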